10.4 STATISTICAL ANALYSES

10.4.1 Analysis of the Primary Endpoints

The fraction of evaluable participants who experience a response will be reported along with a 95% two-sided confidence interval.

10.4.2 Analysis of the Secondary Endpoint(s)

PFS will be determined using the Kaplan-Meier method and will be reported along with 95% confidence intervals. PFS will be defined as the time from the date of first treatment to the date of disease progression or death (any cause) whichever occurs first. Subjects who do not have disease progression or have not died at the end of follow up will be censored at the last known date the subject was progression free.

OS will be evaluated using Kaplan-Meier methods. OS will be defined as the time from the date of first treatment to the date of death (any cause). Subjects who are alive at the end of follow up will be censored at the last known date alive.

Duration of Response: The duration of overall response is measured from the time measurement criteria are met for CR or PR (whichever is first recorded) until the first date that PD or death is objectively documented and is evaluated using the Kaplan-Meier method. Analysis of safety and tolerability is as described in the Section **10.4.3**.

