6. Subsequent Post-treatment follow-up: Every 3 months (+/- 2 weeks), starting after the safety visit for the first year, followed by every 6 months (+/- 4 weeks) for years 2-5, and then annually (+/- 6 weeks) thereafter at the discretion of the investigator. Follow-ups may be done by phone/email or by clinic visit at the discretion of the investigator. Follow-up via telephone/email will include survival, adverse events, and assessment of further tumor therapy; furthermore, routine outside blood, urine, and imaging results may be collected and used for analysis at the discretion of the investigator. Any other evaluations and tests should be performed as clinically indicated. Participants who have not progressed on treatment will be scanned until progression. Those that completed the previous 26-doses course and have progression will be invited for an additional course (26 doses) at the time of progression.
7. Bintrafusp alfa administered IV at flat dose of 1,200 mg.
8. As indicated in Section **12.3**, all subjects will be offered the opportunity to complete an NIH advance directive form. This should be done preferably at baseline but can be done at any time during the study as long as the capacity to do so is retained. The completion of the form is strongly recommended but is not required.
9. Every 6 weeks.
10. Imaging (Section **6.3**) will be performed every 8 weeks (+/- 1 week). In the event of a PR or CR, tumor imaging assessments may be performed every 3 months (+/- 2 weeks) at the discretion of the investigator. Tumor assessment should be continued beyond end of treatment in participants who have not experienced PD until they experience PD in order to assess PFS. Additional imaging to be performed at the investigator's discretion. Imaging performed in outside facilities maybe utilized in the case of travel restrictions or delays, airport closures, inclement weather, family responsibilities, security alerts and government holidays, etc. Nuclear bone scan or imaging may be done for individuals with known/suspected bone lesions at screening; in these cases bone scans should be done in follow-up for response assessments.
11. Optional biopsies: at baseline (within 2 weeks prior to first treatment) and within 2 weeks of first imaging restaging; optional biopsy at/near progression, where clinically feasible.

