12. Where feasible, blood samples for Correlative Research Studies (see Section **5**) will be collected at baseline, W1, W3, W9, and at the EOT. Collection can occur +/- 3 days for any specified timepoint. May also be collected at restaging visits/at time of biopsies per PI discretion.

Where feasible, samples for PK analysis/ADA will be drawn prior to infusion on W1, W3 and W9 and/or with EOT labs if participant comes off treatment prior to any of these timepoints.

13. PET/CT (FDG or Dotatate) scans will be done at screening and at the time of first treatment response evaluation (w8). Then a third one at/near radiographic progression (if there is progression). Effort will be made to keep the same PET/CT type, depending on logistics and availability.

- 14.* Any visits for which administration of trial medication is not planned such as treatment held for AEs, EOT and post-treatment follow-up, assessment may be a telehealth (remote) visit with a member of the study team (e.g., if the patient is not able to return to the NIH CC). Remote visits will be conducted in compliance with NIH guidelines and FDA regulations. A patient may be referred to their local provider or asked to come to the NIH CC for an in-person assessment, if clinically indicated, and at the discretion of the PI. In the case of any visits with participants' local providers, records will be requested. Labs may be drawn locally (interlaboratory variability is not a concern, as these are routine, standardized laboratory tests).
- 15.* Tumor markers (Chromogranin and Neuron Specific Enolase) to be drawn with each restaging.

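### The PFS censoring sentence in 10.4.2 contradicts the PFS event definition by using *or*, and separately does not tie the censoring date to a tumor assessment

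*Combined protocol and SAP*

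**What the plan says.** Section 10.4.2 defines PFS as "the time from the date of first treatment to the date of disease progression or death (any cause) whichever occurs first". The next sentence gives the censoring rule. The group to be censored is "Subjects who do not have disease progression or have not died at the end of follow up will be censored", and the date is given by "censored at the last known date the subject was progression free". OS has its own rule: "Subjects who are alive at the end of follow up will be censored at the last known date alive". Section 6.3.6 repeats the PFS event definition but gives no censoring rule, so 10.4.2 is the only place where one is stated.

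The study calendar (3.7) determines what can be known after treatment:

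- Tumor imaging is marked for the on-treatment weeks (every 8 weeks) and for long-term follow-up. It is not marked for the end-of-treatment or safety visits.
- Footnotes 4 and 5 let those two visits fall back on telephone or email.
- Footnote 6 says of long-term follow-up: "Follow-ups may be done by phone/email or by clinic visit at the discretion of the investigator". The content listed for remote contact is survival, adverse events and further tumor therapy. Progression status is not listed.
- Footnote 14 adds that at "EOT and post-treatment follow-up, assessment may be a telehealth (remote) visit with a member of the study team".
- Footnotes 6 and 10 also say that participants who have not progressed are to be scanned until they do. Footnote 10 gives PFS as the reason.

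**The concern.** The two defects work differently and should be kept apart.

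The first is logical. The definition makes either progression or death sufficient for an event. The censoring sentence makes the absence of either one sufficient for censoring. Both cannot be applied to the same participant. A program that followed the censoring sentence would turn real events into censored observations.

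The second concerns the date. Progression is found mainly by imaging, but the rule does not say how a participant becomes known to be progression free. One analyst could use the last scan without progression. Another could use a later telephone contact at which no progression was reported. The text permits both. The second choice keeps a participant in the risk set while an imaging-detected progression is unlikely to be recorded, which tends to raise the Kaplan-Meier curve.

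**Working it through.** **1. The plan's own figures.** The plan states no number for PFS. Its one checkable probability here is early termination in section 10.2: 0.95^12 = 0.540, matching the stated 54.0%. For the same design (stop at 0/12; 3 or more of 21 is of interest) the exact type I error is 0.080 and the power 0.803, within the stated 0.10 and 0.80. None of these uses PFS.

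**2. The logic of *or*.** The four possible states at the end of follow-up:

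| Progressed | Died | Event definition | Censoring sentence, literally |
|---|---|---|---|
| No | No | No event | Censored |
| Yes | No | Event | Censored (has not died) |
| No | Yes | Event | Censored (no progression) |
| Yes | Yes | Event | Event |

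The two sentences disagree in the middle two rows. Literally applied, an event would require both progression and death.

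**3. Simulation inputs.** From the documents: n = 21 and 8-week scans. Everything else is assumed:

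- exponential time to progression with median 3, 6 or 12 months;
- median post-progression survival 9 or 12 months;
- 24 months of follow-up;
- 10% or 25% of participants stop scanning at a random time in year 1 and remain in contact for 3 or 6 more months.

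That is 3 × 2 × 2 × 2 = 24 scenarios, each with 2,000 runs. The estimate is S(t) = Π(1 − d/n) over event times up to t, averaged over runs. The reference is censoring at the last scan. At 6 months it lies within 0.3 points of the estimate with complete scanning; at 12 months the largest gap is 53.1 − 52.3 = 0.8 points.

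**4. Size of the literal *or*** (percentage points above last-scan censoring):

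- 6-month PFS: from 77.0 − 72.4 = 4.6 to 38.9 − 28.0 = 10.9.
- 12-month PFS: from 13.2 − 7.9 = 5.3 to 41.7 − 27.2 = 14.5.

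An earlier data cut enlarges this, because more progressed participants are still alive. With median PFS 4 months, post-progression survival 12 months and a 12-month cut, 6-month PFS rises from about 38% to 73% in one run, and to about 70% in a repeat with slightly different handling.

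**5. Size of the date defect** (last-contact minus last-scan censoring):

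- 6-month PFS: from 73.0 − 72.5 = 0.5 to 31.6 − 27.7 = 3.9 points.
- 12-month PFS: from 8.4 − 7.8 = 0.6 to 32.0 − 27.2 = 4.8 points.

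A heavier scenario takes median PFS 4 months, post-progression survival 12 months and a 12-month cut. A fraction of participants has no scan after week 8 but is credited through later contact up to the cut. At 6 months:

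| No scan after week 8 | Last scan | Last contact | Gap |
|---|---|---|---|
| 10% | 38.0 | 40.9 | 2.9 |
| 20% | 38.4 | 44.2 | 5.8 |
| 30% | 38.5 | 47.3 | 8.8 |

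Repeat runs gave gaps of about 2.5, 5 and 7.5 points. Crediting contact for only 3 months after the last scan reduces them to about 1.5, 3 and 4.5. If scanning continues until progression, the two rules give the same result.

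**6. Scale.** With n = 21 and PFS near 38%, a simple 95% half-width is 1.96 × √(0.38 × 0.62 / 21) = 0.208, about 21 points.

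**The case against.** The strongest reply is that the plan already separates progression status from mere contact. OS has a different censoring date, and the natural reading of *known* to be progression free is the last assessment that showed no progression. A telephone call that collects survival, adverse events and further therapy does not establish that status. The calendar requires scanning until progression for the sake of PFS, marks imaging in long-term follow-up and allows outside imaging to be used. Footnote 14 permits remote visits but does not waive scans. Unscanned follow-up is therefore a departure from plan. This all stands, and it limits the second defect to cases where scans are missed. It does not remove that defect, because a censoring rule matters most when assessments are missing, and the text leaves the choice open.

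On the *or*, the reply is that the preceding sentence makes the intent clear and few statisticians would program the literal reading. That is probably true, but nothing else in the documents overrides the sentence, and as written it is wrong.

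A reader might infer more than the documents support:

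- That PFS in this trial **is** inflated. The text makes that possible but does not prescribe last-contact censoring.
- That the *or* is what lets unscanned time count. It does not; it would turn events into censored observations.
- That the participants affected are mainly those who stop for toxicity or move to remote follow-up. The documents give no basis for saying who would miss scans.
- That an unscanned participant can have no event except death. Physical examination may form part of tumor assessment (6.3), and outside imaging may be collected.

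**Conclusion.** The point holds in two parts of unequal weight. The *or* is an error as written: it contradicts the event definition in the sentence before it, and if followed literally it would raise 6-month PFS by about 5 to 11 points over 24 months of follow-up, and by much more at an early cut. The undefined basis for the censoring date is a smaller, conditional problem. It could raise 6-month PFS by about 0.5 to 9 points under the assumed scan-stopping scenarios. The top of that range needs 30% of participants unscanned after week 8 and credited through contact up to a 12-month cut. It is zero if scanning follows the calendar.

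All these sizes rest on assumed medians, assumed fractions and scan stopping unrelated to prognosis. PFS here is a secondary, single-arm, descriptive endpoint with no test or target. The sample size, error rates and response-rate decision do not change. The sentence should still be corrected, because PFS is a named secondary objective and in 21 participants a few reclassifications move the curve visibly.

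**What to change.** Replace the censoring sentence in 10.4.2 with: *Subjects with neither documented progression nor death will be censored at the date of their last evaluable tumor assessment (date of first treatment if there is none after baseline); contacts without a tumor assessment do not extend PFS.* Keep the last-known-alive date for OS only.

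This corrects both defects and brings 10.4.2 into line with the calendar's intent that PFS rest on tumor assessment. It costs one sentence and no new data. The price is slightly earlier censoring and possibly a less favourable PFS estimate. Censoring at the last assessment is not a complete remedy: if participants stop scanning because they are deteriorating, it is biased too. The reasons for missed scans should therefore be reported alongside the curve.

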10.4.3 Safety Analyses

The fraction of participants who experience a toxicity, by grade and type of toxicity, will be tabulated. In addition, overall safety will be assessed by descriptive analyses using tabulated frequencies of AEs by grade using CTCAE Version 5 for the study population in terms of treatment-emergent AEs, SAEs, and clinically significant changes in safety laboratory tests, physical examinations, ECGs, and vital signs. Adverse events leading to premature discontinuation from the study intervention and serious treatment-emergent AEs will be presented either in a Table or a Listing.

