3.4 DOSE MODIFICATIONS

3.4.1 Discontinuation

Treatment with bintrafusp alfa will be discontinued in participants experiencing specific adverse events; subjects will remain on study for follow up of survival. Treatment will be discontinued in any participant in the case of:

- Any Grade 4 or higher adverse drug reactions (ADRs) graded according to NCI CTCAE v5.0 and assessed as possibly related to that agent by the Investigator, except for laboratory values that are asymptomatic or resolve to Grade ≤ 1 or baseline grade within 7 days without medical intervention.

- Any Grade 3 ADRs possibly attributed to any agent **except** for any of the following:
 - Transient (\leq 48 hours) Grade 3 nausea and vomiting, headache, flu-like symptoms, fever, controlled with appropriate medical management.
 - Tumor flare phenomenon defined as local pain, irritation, or rash localized at sites of known or suspected tumor.
 - Endocrinopathy that can be medically managed with hormone replacement.
 - Keratoacanthoma and squamous cell carcinoma of the skin. Suspicious skin lesions will be evaluated by dermatology and managed per recommendations (**Appendix B**: Recommendations for Management of IRRs and AEs, Table C), including potential removal of the lesion.
 - Grade 3 laboratory test abnormalities that resolve to Grade \leq 1 or to baseline Grade within 7 days with appropriate medical management or Grade 3 laboratory test abnormalities that are determined not to be clinically significant or asymptomatic.
 - Grade 3 anemia with Hgb <8.0 g/dL that is clinically manageable with PRBC transfusions does not require treatment discontinuation.
 - Any Grade 3 ADR which in the opinion of the investigator is not clinically relevant or can be managed with minimal risk to the participant (e.g. placement of a pleural catheter for recurrent inflammatory pleural effusions).

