3.4.2 Dose delay

- Bintrafusp alfa should be withheld for Grade \geq 2 epistaxis or any Grade \geq 2 toxicity possibly attributed to the study agent until resolution to Grade \leq 1 unless the toxicity in the opinion of the investigator is not clinically relevant or can be medically managed with minimal risk to the participant. Should a clinically relevant grade 2 or 3 toxicity persist for more than 4 weeks, consideration should be given to discontinuing treatment at the discretion of the investigator.
- Laboratory abnormalities which are clinically non-significant and/or unrelated to the agent in the judgement of the investigator, will not lead to dose delays.
- Grade 3 fatigue, headache, nausea, emesis that resolve to Grade \leq 1 with appropriate medical management will not lead to dose delays.
- Management recommendations for infusion-related adverse reactions are found in **Appendix B**: Recommendations for Management of IRRs and AEs, Table A Management of Infusion-related Reactions and should be followed along with institutional standards.
- Immune-related adverse reactions (irAE) should lead to treatment modifications and management per the summarized NCCN recommendations found in **Appendix B**: Recommendations for Management of IRRs and irAEs, Table B Management of immune-related adverse events. Investigators may refer to the relevant guidelines available by ASCO (62), SITC (63), NCCN (64), and ESMO (65).
- For non-medical logistical reasons, unrelated acute illnesses, or palliative radiation, scheduled assessments and dosing can be delayed up to 2 months. Following this interval treatment may resume, and where at all possible, dosing should be restarted to keep in line with the original treatment schedule.

- Local tumor flare phenomenon defined as local pain, irritation, or rash localized at sites of known or suspected lesions will not be considered adverse event or lead to dose interruptions.

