3. Every odd numbered week for up to 51 weeks. Allowance for scheduling changes: Brief changes (up to 1 days earlier or up to 3 days later) in bintrafusp alfa administration and indicated evaluations may occasionally be required due to travel delays or restrictions, airport closure, inclement weather, family responsibilities, security alerts, government holidays, complications of disease not attributable to disease progression or protocol therapy, etc. These delays will not be considered protocol deviation. The timing of subsequent bintrafusp alfa administrations will be adjusted to maintain a minimum interval of 11 days between bintrafusp alfa administrations. Any dose that cannot be accommodated within this window will be skipped and the dose not made up. In the event of a durable PR or CR after one year on trial, further treatment may be held (even if a total of 26 doses has not been given) and scheduled assessments may be performed at 3-month (+/- 2 weeks) intervals at the discretion of the investigator.
4. End of Treatment visit (EOT): within 14 days of the decision to discontinue treatment prematurely before completion of 26 doses. Clinical Center clinic visit preferred; if the participant cannot return to the Clinical Center for this visit, a request will be made to collect required clinical labs (specify as needed) from a local physician or laboratory. If this is not possible, participants may be assessed by telephone/email for symptoms. Does not need to be completed if drug is withheld after 26 doses.
5. 28 days (+/- 7 days) following last treatment. Clinical Center clinic visit preferred; if the participant cannot return to the Clinical Center for this visit, they may be assessed by telephone/email for adverse events.

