6 DATA COLLECTION AND EVALUATION

6.1 DATA COLLECTION

The PI will be responsible for overseeing entry of data into a 21 CFR Part 11-compliant data capture system provided by the NCI CCR and ensuring data accuracy, consistency and timeliness. The principal investigator, associate investigators/research nurses and/or a contracted data manager will assist with the data management efforts. Primary and final analyzed data will have identifiers so that research data can be attributed to an individual human subject participant.

All adverse events, including clinically significant abnormal findings on laboratory evaluations, regardless of severity, will be followed until return to baseline or stabilization of event.

Document AEs from the first study intervention, study day 1, through 28 days after the subject received the last product administration. After 28 days, only adverse events which are serious and related to the study investigational agent need to be recorded.

An abnormal laboratory value will be recorded in the database as an AE **only** if the laboratory abnormality is characterized by any of the following:

- Results in discontinuation from the study
- Is associated with clinical signs or symptoms
- Requires treatment or any other therapeutic intervention
- Is associated with death or another serious adverse event, including hospitalization.
- Is judged by the Investigator to be of significant clinical impact
- If any abnormal laboratory result is considered clinically significant, the investigator will provide details about the action taken with respect to the test drug and about the participant's outcome.

End of study procedures: Data will be stored according to HHS, FDA regulations, and NIH Intramural Records Retention Schedule as applicable.

Loss or destruction of data: Should we become aware that a major breach in our plan to protect subject confidentiality and trial data has occurred, this will be reported expeditiously per requirements in Section [7.2.1](#).

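### Read together, sections 6.1 and 10.4.3 do not require a Grade 3-4 laboratory value that meets no AE trigger to appear in a by-grade safety table (minor, descriptive safety reporting only)

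*Combined protocol and SAP*

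**What the plan says.** Section 10.4.3 makes three commitments. The first is general: "The fraction of participants who experience a toxicity, by grade and type of toxicity, will be tabulated". The second is a count of AEs by CTCAE version 5 grade. The third covers laboratory results beyond AEs, but only as "clinically significant changes in safety laboratory tests, physical examinations, ECGs, and vital signs". The section names no table of measured laboratory values by worst grade and no shift table.

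Section 6.1 decides which laboratory results become AEs. It says "An abnormal laboratory value will be recorded in the database as an AE" and then restricts this to listed circumstances: discontinuation from the study, accompanying signs or symptoms, a need for treatment, association with death or another SAE, or a value that "Is judged by the Investigator to be of significant clinical impact". Grade is not on the list. Section 6.4 ties CTCAE version 5.0 to the reporting of AEs.

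The dosing rules use grade, with exceptions for laboratory values. Section 3.4.1 stops drug for Grade 4 reactions "except for laboratory values that are asymptomatic or resolve to Grade" 1 or baseline within a week without intervention. For Grade 3 it exempts, among others, "Grade 3 laboratory test abnormalities that are determined not to be clinically significant or asymptomatic". Section 3.4.2 adds: "Laboratory abnormalities which are clinically non-significant and/or unrelated to the agent in the judgement of the investigator, will not lead to dose delays".

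**The concern.** Safety and tolerability is a secondary objective (section 1.1.2) of a single-arm, open-label trial, and the by-grade tables are its main planned output. If a high-grade laboratory value reaches those tables only through an investigator's view of its importance, two participants with the same measured value can be counted differently. A reader of the final report could not tell how many such values were set aside.

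Laboratory toxicity is a known feature of this drug. Section 14.1.2 lists ALT, AST, GGT and lipase increases among the related events that led to permanent discontinuation, and gives anemia in 29% and AST elevation in 11% of earlier participants. These are reported events, so they show why laboratory reporting matters here. They do not show how often a high-grade value goes unrecorded.

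**Working it through.** The plan states no figure to reproduce. The check follows one value through the sections, then works out what a single omission would do.

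**Step 1. The value.** Take a Grade 3 or 4 laboratory result that is asymptomatic, untreated, not followed by discontinuation, not associated with death or an SAE, and not judged to be of significant clinical impact.

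| Section | Question | Answer for this value |
|---|---|---|
| 6.1 | Must it be recorded as an AE? | No. None of the five triggers is met. |
| 6.4 | Must it be graded? | Not by this section, which ties grading to AE reporting. |
| 3.4.1 | Must drug stop? | No, under the exceptions for laboratory values. |
| 3.4.2 | Must drug be held? | Not if the investigator judges it non-significant or unrelated. |
| Appendix B, Table B | Any contrary text? | Yes. Under Grade 4 immune-related lymphopenia, an isolated out-of-range value without clinical correlates is called an AE, and drug is held until the cause is known. |
| 10.4.3, AEs by grade | Must it be counted? | No, if it is not recorded as an AE. |
| 10.4.3, laboratory changes | Must it be shown? | No, because it was not judged significant. |
| 10.4.3, first sentence | Must it be counted? | Unclear. Toxicity is not defined as including, or excluding, measured values. |

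No row requires an entry in a by-grade table. Two rows leave room for one. A drug hold is not itself one of the 6.1 triggers, so the Appendix B text does not by itself settle recording.

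**Step 2. Effect of one omission.** If x of n treated participants have a Grade 3-4 laboratory value and one of them is left out, the reported rate falls from x/n to (x - 1)/n, a drop of 1/n.

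- Checkpoint-naïve cohort, n = 21 (section 10.2): 1/21 = 4.8 points.
- Checkpoint-resistant cohort, n = 8 (section 10.2): 1/8 = 12.5 points.
- Cohorts that stop after stage 1: 1/12 = 8.3 points and 1/5 = 20.0 points.

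Sections 10.3 and 10.3.1 base safety on everyone dosed, and the accrual ceiling of 32 allows 3 participants beyond 21 + 8 = 29. If all 3 were checkpoint-naïve, the drop would be 1/24 = 4.2 points; if all 3 were checkpoint-resistant, 1/11 = 9.1 points.

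**Step 3. Number of omissions.** The documents give no frequency. For 0, 1 or 2 omitted participants the shortfall is 0, 4.8 or 9.5 points at n = 21, and 0, 12.5 or 25.0 points at n = 8.

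**Step 4. Availability of data.** The Study Calendar (section 3.7) schedules CBC and biochemistry at odd weeks 1 to 51, which is (51 - 1)/2 + 1 = 26 sets over a full course. Lipase and amylase every 6 weeks from week 1 to week 49 gives (49 - 1)/6 + 1 = 9 sets. A table built from measured values needs no new sampling.

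**The case against.** The best case for the plan is that it already covers these values. The first sentence of 10.4.3 would be largely redundant if toxicity meant only recorded AEs, since AEs by grade are then promised in addition. Section 3.4.2 excepts certain laboratory abnormalities from a rule about toxicity, which is needed only if such abnormalities can be toxicities. Section 3.4.1 carves laboratory values out of reactions graded by CTCAE, which presupposes that they can be graded. Appendix B calls one isolated laboratory finding an AE, and section 8.1.1 allows an abnormal laboratory finding to be one. This stands as a reason for calling the gap possible rather than certain. It does not close the gap, because the restrictive recording rule in 6.1 is the more specific text and 10.4.3 does not say which reading applies.

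A second argument is that 6.1 is a deliberate choice, and that untreated, symptomless values judged unimportant say little about tolerability. That is fair. It supports leaving 6.1 alone and treating this as minor. A third is that the data are collected, the DSMB sees laboratory results (section 7.4.2), and nothing prevents a later table. That is also true, but neither DSMB review nor permission fixes what the final report shows.

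A reader might go further and infer that such a value passes through the whole protocol with no AE and no hold. The documents do not support that as a general statement: Appendix B says otherwise for at least one laboratory event, and the exceptions in 3.4.1 and 3.4.2 permit continued dosing without requiring it.

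**Conclusion.** The point holds as a minor one. Sections 6.1 and 10.4.3 together do not require a Grade 3-4 laboratory value outside the five triggers to enter a by-grade table, so the laboratory toxicity rate may be undercounted in a way that depends on an unblinded judgement. Each participant omitted for this reason costs 1/n of those treated, about 4.8 points at n = 21 and 12.5 points at n = 8. The number omitted is unknown and may be zero.

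The conclusion assumes that the 6.1 list governs what is recorded and that toxicity in 10.4.3 is not meant to include every measured value. If the sponsor intends the wider meaning, only the wording needs to change.

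Two stronger inferences should be resisted. One is that a material undercount is likely: any probability would rest wholly on an assumed rate, since the documents give none. The other is that efficacy or care is compromised. Response rate and the two-stage decision do not use these tables, and values that are symptomatic, treated, judged significant, or linked to discontinuation, death or an SAE are already captured.

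**What to change.** Add one table to 10.4.3, for all treated participants and by cohort, showing worst post-baseline CTCAE version 5.0 grade and shift from baseline grade. Specify that it:

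- covers the scheduled CBC, biochemistry and hepatic panel, lipase and amylase;
- is derived from all available values from first dose through 28 days after last dose, the AE window in 6.1, regardless of AE status;
- takes the last value before first dose as baseline;
- shows missing values as missing, with the number of participants who have no post-baseline value for each test;
- is labelled as laboratory abnormalities without attribution, separate from the AE-by-grade table, which should be stated to count recorded AEs.

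Leave the recording rule in 6.1 unchanged and keep the clinically significant changes already planned.

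The cost is a paragraph of SAP text, a little programming, and normal ranges for samples drawn elsewhere. Footnote 14 to the Study Calendar allows local laboratories, and footnote 4 says that, for a participant who cannot return at end of treatment, "a request will be made to collect required clinical labs (specify as needed) from a local physician or laboratory". Some late values will be missing, because the end-of-treatment and safety visits may be done by telephone or email. The reported laboratory toxicity rate may look less favourable, and the report will carry a second high-grade rate beside the AE rate, which is why the label matters. Visits, AE recording and care do not change.
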